8. Be willing to not increase pain medications from baseline through the 3-Month Visit
9. Be willing and able to comply with study-related requirements, procedures, and visits

B.3.3. Exclusion Criteria

In order to participate in the study, a subject must *NOT* MEET ANY of the following exclusion criteria:

1. Had a previous spinal surgery (e.g., lumbar fusion, discectomy, laminectomy, laminotomy)
2. Has a medical, anatomical, and/or psychosocial condition that is contraindicated for commercially available Intellis™ SCS systems as determined by the Investigator
3. Has a diagnosed back condition with inflammatory causes of back pain (e.g., onset of severe pain with activity), serious spinal pathology and/or neurological disorders as determined by the Investigator
4. Be concurrently participating in another clinical study
5. Has an existing active implanted device such as a pacemaker, another SCS unit, peripheral nerve stimulator, and/or drug delivery pump, etc.
6. Has pain in other area(s) and/or medical condition requiring the regular use of significant pain medications that could interfere with accurate pain reporting, study procedures, and/or confound evaluation of study endpoints, as determined by the Investigator
7. Has mechanical spine instability as determined by the Investigator
8. Has undergone, within 30 days prior to enrollment, an interventional procedure and/or surgery to treat back and/or leg pain, which is providing significant pain relief
9. Has unresolved major issues of secondary gain (e.g., social, financial, legal), as determined by the investigator
10. Be involved in an injury claim under current litigation or has a pending or approved worker's compensation claim
11. Be pregnant (determined by urine testing unless female subject is surgically sterile or post-menopausal. If female, sexually active, and childbearing age, subject must be willing to use a reliable form of birth control.)

B.4. Treatment Groups

Subjects meeting the study entrance criteria will be randomized to one of two study treatment groups in a 1:1 ratio:

- Control Treatment Group: Conventional SCS programming approach
 - Stimulation parameters in the 40-250 Hz frequency range will be trialed according to standard practice as described in the Intellis™ labeling/manuals
 - If frequency parameter above 250 Hz is used during the study, the subject will be counted as failure towards Conventional SCS programming approach but will continue to permanent implant.

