B.7. Study Endpoints

B.7.1. Definition of Analysis Populations

- Modified Intent to Treat (mITT): All successfully randomized subjects who complete the Trial Phase.
- Intent-to-Treat (ITT): All successfully randomized subjects who met all the enrollment criteria.
- Per-Protocol (PP): All subjects who received a permanent device implant and contributed their data to the 3-month endpoint without any major protocol deviations or adverse events (that would render their data unevaluable).

The primary analysis of the primary and secondary endpoints will be performed on the mITT population. Supportive analyses will be performed for the Intent-to-Treat and Per-Protocol population.

For analyses incorporating crossover data (i.e. data gathered in the post 6-month periods), analyses will be based on the mITT population with treatment group defined by the treatment status at the corresponding time point to capture the impact of crossover. Additional sensitivity analyses censoring data post-crossover will be performed to examine the impact of crossover.

B.7.2. Effectiveness Assessment Definitions

- Primary Effectiveness Assessment: For subjects who have a successful Trial Phase and receive a permanent implant, the Primary Efficacy Assessment occurs at the follow up visit 3 months after Device Activation. For subjects who do not have a successful Trial Phase (based on subject's pain score) or subjects who do not want a permanent device implant due to insufficient pain relief (based on subject's discontinuation reason), the Primary Efficacy Assessment occurs at the end of the Trial Phase.

B.7.3. Primary Endpoint

Pain rating on the 10 cm Visual Analog Scale is considered the primary outcome measure. VAS is the most widely used outcome measure in assessing pain due to its documented reliability and validity, ease in administration, and minimal training requirements for the administrator.

- ***Individual Responder:*** A decrease in back pain VAS by at least 50% at 3 months after Permanent Device Activation as compared with Baseline. All subjects must be using the assigned programming parameters. If a subject is switched to a programming parameter that is not considered to be DTM-SCS nor Conventional SCS programming the subject will be counted as a non-responder for the following follow-up visit if one of the two following conditions exist:

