 - If a subject is switched to a programming parameter that is not considered to be DTM-SCS nor Conventional SCS programming for a period over two weeks
 - If a subject is switched to a programming parameter that is not considered to be DTM-SCS nor Conventional SCS programming for any length of time within the 2 weeks prior to a follow-up visit.

Overall Study Success: The percentage of Individual Responders in the test group is shown to be statistically non-inferior to the percentage in the control group.

B.7.4. Secondary Endpoints

The following secondary endpoints will be evaluated:

- Comparison of the percentage of Individual Responders between the test and control groups in a statistical test of superiority over time (i.e. based on repeated measures analysis). In addition, data will be summarized at the individual time points at 3 months, 6 months, 9 months, and 12 months. This will be performed based on all observed data with treatment defined as a time dependent covariate, and additionally based on censoring data post-crossover.

- Comparison of change from Baseline in back pain score (VAS) between test and control in statistical tests of non-inferiority and superiority. This is calculated as: Change from Baseline in Back Pain VAS = Follow-up Visit Pain VAS – Baseline Pain VAS. A negative result reflects a decrease in the Pain VAS, while a positive result reflects an increase in Pain VAS. All subjects must be using the assigned programming parameters. If a subject is switched to a programming parameter that is not considered to be DTM-SCS nor Conventional SCS programming, that subject's Baseline Back Pain VAS will be used instead of Follow-up Visit VAS after the programming change has occurred for the following follow-up visit if one of the two following conditions exist:
 - If a subject is switched to a programming parameter that is not considered to be DTM-SCS nor Conventional SCS programming for a period over two weeks
 - If a subject is switched to a programming parameter that is not considered to be DTM-SCS nor Conventional SCS programming for any length of time within the 2 weeks prior to a follow-up visit.

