Analysis of both secondary endpoints will be based on a repeated measures approach that accounts for within subject correlation. Treatment group status for the repeated measures models will be based on treatment status at the current time point (i.e. it will be based on treatment status incorporating potential crossover, not necessarily the original randomized assignment).

B.7.5. Additional Data Collection

These following data will be collected:

- Frequency of treatment emergent adverse events
- Comparison of opioid medication usage from baseline at 3, 6, 9 and 12 months after device activation between the two arms
- Comparison of mean change from Baseline in Leg Pain VAS, evaluated at 3, 6, 9 and 12 months after device activation for subjects with baseline leg pain VAS score ≥ 5 between test and control
- Comparison of Leg Pain Treatment Success, measured as at least a 50% reduction in Leg Pain VAS, evaluated at 3, 6, 9, and 12 months after device activation for subjects with baseline leg pain VAS score ≥ 5 between test and control
- Comparison of patient satisfaction between two arms
- Patient Global Impression of Change, evaluated at 3, 6, 9 and 12 months after device activation
- Comparison of Patient Global Impression of Change between two arms

- Comparison of ODI change from baseline at 3, 6, 9 and 12 months after device activation between the two arms
- Comparison of quality of life (QoL) change (from EuroQol EQ-5D-5L) from baseline at 3, 6, 9 and 12 months after device activation between the two arms
- Quality of paresthesia at 3, 6, 9 and 12 months, comparison between test and control
- Percentage of subjects that crossover
- Comparison of mean change from last visit prior to crossover to 12 months visit. This analysis censors data post-crossover.
- Activity level based on Intellis™ adaptive data log (when available)
- Analysis of additional evaluable data items will be based on treatment status at the current time point (i.e. it will be based on treatment status incorporating potential crossover, not necessarily the original randomized assignment).

B.8. Evaluation Criteria

B.8.1. Effectiveness

Results of the tests and standard questionnaires will be recorded in Case Report Forms at Baseline and during follow-up visits. Changes from Baseline will be calculated and compared between the two groups.

Effectiveness will be measured for each subject using the following tests:

- Pain

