Activity	Pre-Trial Phase			Trial Phase		Permanent Implant (up to 60 days after end of trial)	Permanent Implant Phase Follow-up					
	Enrollment	Baseline	Randomization	Start Trial Phase	End Trial Phase (up to 10 days after start of trial)		Device Activation (0-14 days after implant)	1-month visit (±15 days after activation)	3 months visit (±21 days after activation)	6 months visit (±31 days after activation)	9 months visit (±31 days after activation)	12 months visit (±45 days after activation)
Informed Consent	X											
Pain Intensity Evaluation (VAS)	X				X			X	X	X	X	X
Medication Use	X	X		X	X	X	X	X	X	X	X	X
Medical/Surgical History	X	X										
Eligibility Criteria Evaluation	X											
Disability Assessment (ODI)	X							X	X	X	X	X
Quality of Life Assessment (EQ-5D-5L)		X						X	X	X	X	X
Randomization			X									
AP/Lateral x-ray imaging				X	[X]	X	[X]	X	[X]	[X]	[X]	[X]
Paresthesia Questionnaire								X	X	X	X	X
Patient Global Impression of Change								X	X	X	X	X
Subject Satisfaction								X	X	X	X	X
Adverse Event Monitoring	X		X	X	X	X	X	X	X	X	X	X
Device Programming				X		X	[X]	[X]	[X]	[X]	[X]	[X]
Device Log								[X]	[X]	[X]	[X]	[X]
Cross over									[X]			
Study Completion					X ^a							X

^a For subjects that do not have a successful Trial Phase.

[X] Optional activity.

B.9.2. Statistical Analysis

Descriptive statistics will be used to summarize baseline and outcome data collected during the study. Continuous variables will be summarized using means, standard deviations, and ranges. Categorical variables will be summarized in frequency distributions. Repeated measures models will account for within subject correlation by use of a compound-symmetric covariance structure (based on logistic regression/generalized estimating equations for binary variables, and linear repeated measures models for continuous variables).

B.9.2.1 Primary Analyses

The *primary efficacy endpoint* will be evaluated with a Farrington-Manning binomial test for non-inferiority with a 10% margin at the one-sided 0.05 alpha level.

H_0 : The percentage of subjects (P) who achieve a 50% improvement in their back VAS pain score at 3 months in the Test group is inferior to that in the Control group.

$$P_{\text{Test}} \leq P_{\text{Control}} - 10\%$$

H_1 : The percentage of subjects (P) who achieve a 50% improvement in their back VAS pain score at 3 months in the Test group is not inferior to that in the Control group.

$$P_{\text{Test}} > P_{\text{Control}} - 10\%$$

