The following secondary endpoints do not have an associated hypothesis, and no significance level will be assigned to statistical tests that may be performed. Analysis of these endpoints will be based on a repeated measures approach that accounts for within subject correlation. Treatment group status for the repeated measures models will be based on treatment status at the current time point (i.e. it will be based on treatment status incorporating potential crossover, not necessarily the original randomized assignment).

- Comparison of Back Pain Treatment Success (responder rate), measured as subjects with at least a 50% reduction in Back Pain VAS, between test and control
- Comparison of mean change from Baseline in Back Pain VAS, between test and control

B.9.2.3 Additional Data

- Comparison of Leg Pain Treatment Success (responder rate), measured as subjects with at least a 50% reduction in Leg Pain VAS, between test and control for subjects with baseline leg pain VAS score ≥ 5
- Comparison of mean change from Baseline in Leg Pain VAS, between test and control for subjects with baseline leg pain VAS score ≥ 5
- *Satisfaction with Therapy*: Subject Satisfaction will be compared between test and control
- *Patient Global Impression Change*: The Patient Global Impression of Change from Baseline to follow-ups at 3-, 6-, 9- and 12-month visits after device activation will be compared between the treatment groups.

- *Oswestry Disability Index (ODI)*: The changes in ODI from Baseline to 3-, 6-, 9- and 12-months will be summarized as continuous variables and compared between the treatment groups.
- *Quality of Life*: The changes in the EQ-5D-5L instrument from Baseline to follow-ups at 3-, 6-, 9- and 12-months will be summarized as continuous variables and compared between the treatment groups.
- *Paresthesia Questionnaire*: Questions about the paresthesia will be used at 3-, 6-, 9-and 12-month visits and compared between test and control

B.9.2.4 Handling of Missing Data

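### No specified 9- or 12-month analysis compares subjects by randomized arm: data are grouped by current treatment or censored at crossover, and crossover follows insufficient relief

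*Combined protocol and SAP*

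**What the plan says.** - **Who crosses (B.6.1, B.6.14).** Crossover is optional and two-way. It opens once the month-6 assessment is done and must be completed within 30 days. It is for subjects without sufficient relief who want to try the other arm's programming.
- **Grouping after month 6 (B.7.1).** The mITT population is used, with "treatment group defined by the treatment status at the corresponding time point to capture the impact of crossover". The only alternative is: "Additional sensitivity analyses censoring data post-crossover will be performed to examine the impact of crossover". Supportive ITT and per-protocol analyses are also named. ITT is defined by membership (randomized and meeting the entry criteria).
- **Secondary endpoints (B.7.4, B.9.2.2).** For responders: "This will be performed based on all observed data with treatment defined as a time dependent covariate, and additionally based on censoring data post-crossover". B.7.4 also orders summaries at 3, 6, 9 and 12 months. On treatment group in the repeated-measures models for both endpoints, the two sections say that "it will be based on treatment status incorporating potential crossover, not necessarily the original randomized assignment".
- **Other outcomes (B.7.5, B.9.2.3).** "Analysis of additional evaluable data items will be based on treatment status at the current time point". This covers leg pain, ODI, EQ-5D-5L and the rest. B.9.2.3 says that changes in ODI and EQ-5D-5L "will be summarized as continuous variables and compared between the treatment groups", without saying whether a repeated-measures model is used.
- **Model (B.9.2).** "Repeated measures models will account for within subject correlation by use of a compound-symmetric covariance structure", by GEE for binary outcomes and a linear model for continuous ones.
- **Status.** B.9.2.2 gives the longitudinal comparisons no hypothesis or significance level, and B.8.2 sets no secondary success criterion. The separate SAP is cited in B.9.2.4 for imputation only.

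**The concern.** Randomization protects a comparison only while subjects are counted in the arm to which they were assigned. Here a poor outcome is the condition for changing group. Grouping by current treatment moves subjects selected for poor relief into the other column. Censoring keeps the randomized labels but removes those subjects' 9- and 12-month visits. Subjects are unblinded (B.5.4), so the share of non-responders who cross need not be the same in the two arms. At stake is how the 9- and 12-month results can be read: a raw difference may appear where none exists, and a real one may be understated. Two wording faults in the same sections add to this: one crossover item cannot be computed for crossers as written, and B.7.4 and B.9.2.2 disagree on which secondary comparisons are formal tests.

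**Working it through.** **1. Text.** Each post-month-6 rule in B.7.1, B.7.4, B.7.5 and B.9.2.2 assigns group by current treatment or censors at crossover. None assigns it by randomized arm regardless of crossover.

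**2. Inputs.** The plan has no figure to reproduce here: it gives no crossover rate, trial-failure rate or model terms. From B.5.5.1 I take 70% and 50% response. Assumed: only implanted month-6 non-responders cross; trial failures (0 or 20%) are non-responders throughout and cannot cross; overall response is held at target; switching has no effect; percent relief has subject SD 25 and residual SD 15, so its correlation between visits is 625/(625 + 225) = 0.735.

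**3. Formulas, per 100 subjects per arm.** R = responders, F = trial failures, x = fraction of implanted non-responders crossing, q = chance that a month-6 non-responder responds at month 12.
- Crossers: k = x(100 - F - R). Crossers responding at month 12: c = qk.
- Censored rate in an arm: (R - c)/(100 - k).
- Current-treatment rate, DTM: (R_D - c_D + c_C)/(100 - k_D + k_C). Conventional is the mirror image.
- At 50% response, q = 1 - 2[1/4 + arcsin(0.735)/(2π)] = 0.237. The same bivariate normal gives 0.300, 0.342 and 0.474 at 62.5%, 70% and 87.5% response among the implanted.

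**4. Raw month-12 results (DTM minus Conventional).**
- *No true difference, 50% response, 20% (DTM) vs 60% (Conventional) crossing, no failures.* k = 10 and 30; c = 2.37 and 7.11. Current treatment: 54.74/120 - 45.26/80 = 45.6% - 56.6% = -11.0. Censored: 47.63/90 - 42.89/70 = about -8.3.
- *Same, 20% failures* (50/80 = 62.5% of the implanted respond). k = 6 and 18; c = 1.80 and 5.40. Current: 53.60/112 - 46.40/88 = -4.9. Censored: 48.20/94 - 44.60/82 = -3.1.
- *Equal crossing:* both 0. *Crossing reversed (60% vs 20%):* signs reverse.
- *70% vs 50%, half crossing, no failures.* k = 15 and 25; c = 5.13 and 5.93. Current: 70.80/110 - 49.20/90 = +9.7. Censored: 64.87/85 - 44.07/75 = +17.6.
- *Same, 20% failures.* k = 5 and 15; c = 2.37 and 4.50. Current: 72.13/110 - 47.87/90 = +12.4. Censored: 67.63/95 - 45.50/85 = +17.7.

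**5. Repeated-measures models.** A simulation under these assumptions (60,000 per arm, visits 3 to 12, exchangeable logistic GEE with treatment-by-visit terms) gave the following, in points:

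| Case | Raw current / censored | GEE current / censored | Randomized arm |
|---|---|---|---|
| Null, 20/60, no failures | -11.1 / -8.5 | -0.1 / -0.2 | 0 |
| Null, 20/60, 20% failures | -5.1 / -3.4 | +2.5 / +0.9 | 0 |
| 70/50, half cross, no failures | +9.5 / +17.3 | +6.7 / +19.5 | +20 |
| 70/50, half cross, 20% failures | +12.3 / +17.5 | +10.4 / +20.6 | +20 |

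A compound-symmetric linear model on percent relief, with a true difference of 15.5, gave 3.4 by current treatment and 15.5 censored.

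**6. If switching works.** Turning 30% of control crossers into responders moves the randomized-arm +20 to between +14 and +17; 60% moves it to between +8 and +13.5. In a separate simulation (relief SD 35, correlation 0.6), crossers took on the full mean effect of the new programming and the difference without crossing was +20.2:

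| Non-responders crossing | Raw current | Raw censored | Randomized arm |
|---|---|---|---|
| 50% in both arms | +19.1 | +18.3 | +11.2 |
| 50% control, 10% DTM | +11.9 | +14.3 | +13.9 |
| 10% control, 50% DTM | +26.8 | +24.0 | +15.8 |

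**7. Related wording.**
- B.7.5 asks for change from the last pre-crossover visit to month 12 and, in the same item, censors post-crossover data. A crosser then has no month-12 value.
- B.7.4 calls the repeated-measures responder comparison a superiority test and names both non-inferiority and superiority tests for VAS change. B.9.2.2 gives the repeated-measures comparisons no hypothesis, and its formal VAS test at 3 months is non-inferiority only.

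**The case against.** The strongest reply is that the plan already contains a good analysis. Crossover follows the month-6 assessment, the earlier visits stay in the model, and the censored repeated-measures model recovers close to 0 or +20 above. A randomized-arm comparison answers a different question (assignment including later switching) and is diluted if switching works. The -11 needs a threefold difference in crossing and no trial failures, neither of which is in the documents; with 20% failures the raw bias is half a standard error or less. The plan is also open about its grouping rule. All of this stands. It confines the concern to the current-treatment analysis and the raw summaries, and makes the randomized-arm result an addition. It does not supply the missing comparison.

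The supportive ITT analysis might be thought to supply it. It does not: it fixes membership, while the post-month-6 rule fixes grouping.

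Two stronger readings are tempting and not supported:
- *That crossers are scored as non-responders, or given their baseline VAS, under B.7.3 and B.7.4.* That penalty applies only to programming that is neither DTM-SCS nor Conventional SCS. A crosser uses one of the two.
- *That control crossers are automatic failures under B.4:* "If frequency parameter above 250 Hz is used during the study, the subject will be counted as failure towards Conventional SCS programming approach". The sentence goes on to say that the subject proceeds to permanent implant, which points to the Trial Phase. Only the reference to the whole study needs reconciling with permitted crossover.

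**Conclusion.** The concern holds in limited form. No 9- or 12-month analysis by randomized arm is specified, and crossover depends on outcome, so the raw current-treatment and censored summaries are not randomized comparisons. Their bias can go either way and is 0 under the null with equal crossing. Under the stated assumptions it is about -11 and -8 points with 20% vs 60% crossing, falling to about -5 and -3 with 20% trial failures. A true +20 appears as about +10 to +12 by current treatment and +17 to +18 censored. That attenuation by current treatment assumes that switching has no effect; if switching carries the full effect and crossing is equal, the raw current-treatment figure is near +19. For scale, the standard error at 50% response and 50 per arm is √(2 × 0.25/50) = 10 points. The censored repeated-measures model is close to the no-switching difference in these simulations.

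A reader might infer that the trial's main conclusion is at risk. It is not: crossover starts after month 6, so the primary endpoint, the 3-month tests, the month-6 comparison and study success are untouched, and the longitudinal comparisons carry no hypothesis.

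**What to change.** 1. In B.7.1, B.7.4, B.7.5 and B.9.2.2, add a descriptive 9- and 12-month comparison of observed mITT data by randomized arm regardless of crossover, beside the two planned results.
   - Label current-treatment results as non-randomized, and censored results as dependent on outcome-related crossover.
   - Name month 6 as the last pre-crossover comparison.
   - State that the randomized-arm result is diluted if switching works, and may still lose subjects withdrawn at crossover for lead migration (B.6.14).
   - State that, in this analysis, crossers to the other study programming are scored on observed values in both directions. Reconcile the study-wide wording in B.4 with permitted crossover.
2. Correct the B.7.5 crossover item: either use post-crossover data through month 12, reported by direction of crossover, or restate it as change up to the last pre-crossover visit.
3. Reconcile B.7.4 with B.9.2.2 on which secondary comparisons are formal tests, including whether VAS superiority is tested or descriptive.

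Cost: wording changes and one extra table set from data already collected. No sample-size figure changes. The downside is a diluted randomized-arm estimate if switching works, which is why it is added and replaces nothing.
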